12.2 Planned recruitment rate

We will aim to recruit on average 55 participants per month. Recruitment rates will be monitored monthly and additional sites will be recruited if needed. The first six months of the recruitment period will be assigned as an internal pilot to assess recruitment rates and risks of contamination. If the pilot phase is successful, it will also constitute the first six months of the 21-month recruitment period. The table below outlines how overall recruitment within the first 6 months of the trial recruitment period should be assessed by the Trial Steering Committee (TSC), in conjunction with the co-ordinating trial centres.

	GREEN	AMBER	RED
Primary criteria – Monthly recruitment rate	Reaches 100% at months 5 & 6	Between 60-100% at months 5 & 6	<60% at months 5 & 6
Outcome	Maintaining this rate will achieve trial target sample size	Present action plan to TSC with clear and achievable strategies for overcoming identified recruitment barriers and/or recruit extra trial centres. TSC to manage this plan without referring to HTA. TSC to formally assess recruitment again in 6 months (12 months into trial).	Rescue plan will be considered by TSC and HTA commissioning board; monitoring visit from HTA; joint decision on whether trial should be modified or continued

As part of the pilot we will also monitor contamination rates, i.e. the QN arm using EC (EC arm use of QN is less likely, but this too will be monitored). Contamination will be defined as any use of EC (even just a puff) daily for five consecutive days within the first four weeks post-TQD in the QN study arm; and any use of QN in the two EC arms. If contamination rate in the QN study arm during the first 4-weeks post-TQD is greater than 20% and remedial actions do not change this by the sixth month of the

pilot, the QN study arm may be terminated. The decision will be made in consultation with the TSC and funder (HTA).

To minimise contamination we will ask participant to agree to the terms of a commitment form, requiring that they do not use non-allocated products in the first four weeks. Participants will be asked to confirm their commitment via a text or e-mail. We used this approach in our previous studies and it is likely to have contributed to very low contamination rates that we had.

We are focusing on contamination risk over the initial 4-week period because product switches later on are most likely in smokers who did not manage to stop smoking with allocated product help. As the primary outcome concerns sustained abstinence from 2 weeks post-TQD, participants who still smoke after this period will be classified as smokers regardless of product treatment use and so any later contamination will not affect the primary outcome result.

12.3 Method of analysis

All analyses will be carried out by the trial statistician.

To describe participants' demographic and smoking characteristics at baseline by arms, descriptive statistics will be presented using mean and standard deviation for continuous measures that are approximately symmetric; median and quartiles if the distribution is skewed. Discrete outcomes will be described using both the number and proportion (percentage). Similarly, summary measures of the primary and secondary outcomes will be presented.

Analyses of abstinence will use intention-to-treat (ITT) principle with participants lost to follow-up or not providing biochemical validation included as non-abstainers/non-reducers (no change in cigarette consumption). However, sensitivity analyses will be conducted to assess the robustness of conclusions to missing outcome data (complete case analysis, multiple imputation) and departures from randomised treatment (per protocol analysis).

In smoking cessation trials, data are not missing completely at random – smokers who fail in their quit attempt typically avoid follow-up contact while those who succeed are keen to attend. Participants lost to follow-up will be included as smokers.

As our analyses focus on two pairwise comparisons (QN vs. EC and EC vs. EC+ arms), we will use a Bonferroni adjustment to account for multiple testing and reduce type I error ($\alpha = 0.05/2 = 0.025$).

12.4 Statistical analysis plan (SAP)

For the primary outcome, the proportion of people remaining abstinent at 6 months will be reported by study arm and compared using a binomial regression with a log

link. This will allow us to estimate the risk ratio. The number needed to treat (95%CI) will also be estimated based on the results of the primary endpoint.

For the secondary abstinence endpoints, we will examine the differences between study arms in the proportions of participants with CO-validated sustained abstinence at 4, 6 months and 1 year. We will compare the frequency of respiratory symptoms at follow-up between study arms while adjusting for baseline. The frequency of adverse events (AEs) and events deemed as adverse reactions to e-cigarettes (ARs) and respiratory symptoms will be compared between arms. The MedDRA coding system will be used for safety information data.

These secondary outcomes are all binary and therefore we will use general linear model with family set as binomial with a log link to estimate risk ratios. If the models fail to converge, we will use general linear model with family specified as binomial with a log link and robust standard errors. If this also fails, we will run a chi-square test and calculate risk ratios (95%CI).

We will also explore differences in the number of cigarettes per day smoked at each follow-up point in non-abstainers and by vaping status using linear regression while adjusting for baseline scores. Similarly, differences in weight at follow-up will be compared at each follow-up using linear regression adjusting for baseline scores. Lastly, urges to smoke and withdrawal symptoms at 4 weeks will be compared by arms while adjusting for baseline scores

Descriptive statistics will be presented to summarise adherence to treatment. For EC use, this will be indexed by whether EC are used at each time point, on how many days per week and the volume of e-liquid per week, and when not used any longer, how long after the TQD the use was stopped. We will also record reasons for stopping use. Types of EC devices and nicotine content and flavours of e-liquids will be recorded at each time point. In the EC+ arm, we will record how many support calls were completed. Regarding QN, we will record whether participants opted for daily texts, e-mails or both, whether they report that they allowed the messages for the full 28-days duration and if not, how long after the TQD they opted out; how many times they report visiting the website; and whether they used any of QN recommendations.

A detailed description of the analysis will be provided in the statistical analysis plan to be agreed with the trial steering and management committees and finalised prior to completion of data collection.

Analysis Timeline

Analysis will be carried out in 2 stages. The first stage is an analysis for primary and secondary endpoints once 6 months data collection is complete. This will require a soft data lock of the database. The data will be cleaned and extracted to allow analysis. The database will, nonetheless, remain live to allow collection of 12 month data.

Once the collection of 12 month outcomes are complete, these data will be cleaned and the dataset will be locked (i.e. hard data lock).

13. Qualitative study

An embedded qualitative study will address the third research question: What are the barriers and facilitators to referral by HCPs of smokers interested in EC to the EC helpline, and for smokers using it? The study will involve semi-structured interviews with 20 HCPs and 20 smokers, including HCPs and smokers who were and were not involved in the trial.

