9.3 Randomisation and blinding

Randomisation (1:1:1) in permuted blocks will be undertaken using a web-based application. There are no stratification factors. As there are 3 treatment groups, the study may use blocks of a minimum size of 9 and a maximum of 18. The trial statistician will produce the randomisation list, which will be embedded into an application that only reveals the next treatment assignment once a participant has been entered into the database. We will use REDCap as the randomisation application which will be hosted by Kings College London (KCL) (a secure system currently used by both Queen Mary University of London (QMUL) and KCL).

Participants who are eligible and consent to take part will be randomly allocated to the experimental or control interventions at baseline. Staff will access the web-based application when the participant is on the phone with them, which will generate a unique participant ID number. The randomisation allocation will immediately be provided by the program and the participant advised of it.

Due to the nature of the trial, the intervention allocation cannot be blinded to participants. We will try to limit expectation effects by recruiting only participants with no strong treatment preference; and by emphasising in the PIS that the relative efficacy of the three treatment options is not known. Staff collecting follow-up data will be blind to treatment allocation until questions are reached that reveal allocation.

10. Schedule for treatment for each visit

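### The SAP deadline is set at the end of data collection, which read literally falls about six months after the 6-month primary data are complete and ready to be analysed by arm

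*Protocol*

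**What the plan says.** Section 12.4 leaves the detailed analysis to a SAP that is to be "agreed with the trial steering and management committees and finalised prior to completion of data collection". It names no date, time point or lock.

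The Analysis Timeline in the same section has two stages. For the earlier one it says "The first stage is an analysis for primary and secondary endpoints once 6 months data collection is complete". On the lock, it adds "This will require a soft data lock of the database", after which data are cleaned and extracted for analysis. Collection goes on beyond that point: "The database will, nonetheless, remain live to allow collection of 12 month data". The hard lock follows once the 12-month outcomes have been collected and cleaned. Section 10.5 places the end of the study at the last attempt to obtain 12-month data from the last person randomised.

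Section 12.4 also says that 6-month abstinence is reported and compared by arm. On who does the work, section 9.3 says "The trial statistician will produce the randomisation list" and section 12.3 says "All analyses will be carried out by the trial statistician".

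**The concern.** A SAP protects against result-driven choices only if it is fixed before anyone has seen the comparison it governs. Here the comparison that matters most is made at the first stage, but the SAP deadline is attached to an event that, on the plain wording, belongs to the second stage. A team could follow the text exactly and still settle open analysis choices with the primary answer in hand.

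Other stated safeguards do not close this gap. Participants cannot be blinded, one statistician both generates the allocation list and runs every analysis, and no section requires sign-off before the 6-month extraction.

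The point is not that SAP detail is absent from the protocol. The protocol states a milestone for the SAP, and the milestone is set too late.

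**Working it through.** **1. The protocol's own end date, from its own inputs** (synopsis, Study duration)

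- Recruitment starts 1/3/2021 and lasts 21 months, so it ends 30/11/2022.
- Adding 12 months of follow-up gives 30/11/2023. This matches the stated date of last follow-up.

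**2. When the primary data are complete**

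- The primary endpoint is at 6 months (section 6.4): 30/11/2022 + 6 months = 30/5/2023.
- From 30/5/2023 to 30/11/2023 is 184 days, about six months.
- These dates count from the end of recruitment. The target quit date falls some days later and moves both dates equally, so the gap is unchanged.

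**3. How long the result could be known before the deadline passes**

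- The protocol gives no time for cleaning and analysis after the soft lock. Assume 1 to 3 months.
- 6 − 1 = 5 months and 6 − 3 = 3 months. About 3 to 5 months would remain in which the primary result exists and the literal SAP deadline has not passed.

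**4. Which data collection is meant**

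- The SAP sentence says "finalised prior to completion of data collection", without qualification.
- Where the authors mean the 6-month data, in the timeline that follows, they say so.
- The database stays live for 12-month data, and section 10.5 ends the study with the 12-month attempts. Data collection as a whole is therefore complete only at 12 months.

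**5. What is already fixed, and what is open**

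| Item | Status in the protocol |
|---|---|
| Primary endpoint, abstinence definition and CO cut-off | Fixed (6.4, 6.5) |
| No biochemical validation or lost to follow-up | Fixed as non-abstinent (6.5, 12.3) |
| Two comparisons, alpha 0.05/2 = 0.025 | Fixed (12.3) |
| Primary model: binomial regression with log link, risk ratio | Fixed (12.4) |
| Per-protocol definition, imputation model | Analyses named, not defined (12.3) |
| Fallback if the primary model does not converge | Open: the fallback in 12.4 is written for the secondary outcomes |
| Whether a validated 12-month contact can change 6-month status | Open: 6.5 counts as abstainers people without contact or CO validation at one contact but validated at the next, and does not say how this works across the soft lock |
| Details of secondary analyses | Partly open (12.4) |

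The per-protocol and imputation items bear only on sensitivity analyses. The fallback could affect the primary estimate, and the later-contact rule could affect the primary count.

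**The case against.** The best reply is that the sentence sets an outer limit. A SAP finalised before the 6-month data are complete satisfies it, and since the SAP is to describe the analysis and the first stage is an analysis, the authors may well have intended the earlier date. The SAP was not available for this review and may have been signed in good time. That stands as a limit: the criticism is of what the wording permits, not of what was done. It does not rescue the wording, because the natural reading is the later date.

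The second reply is that the main analysis is largely protected by the protocol itself. The SAP also needs the agreement of a steering committee that has an independent chair and an independent statistician (section 21). This stands too, and it lowers the severity.

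A reader might infer more than the documents support:

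- *That the treatment of missing CO could be chosen after the result.* It could not. Sections 6.5 and 12.3 fix it for the abstinence analyses.
- *That the primary analysis is declared unblinded.* The protocol does not use that term. It is an inference from a by-arm comparison run by the person who produced the list.
- *That 28% of participants are exposed.* At 55 per month, 6 × 55 = 330 of 1,170 have a 12-month contact still to come when 6-month data are complete. But results exist only after cleaning and analysis, and those contacts serve 12-month outcomes. The figure is an upper bound on something else, not a measure of this problem.
- *That 6-month results must be kept from follow-up staff until the hard lock.* Callers start blind to allocation (section 9.3), and sustained abstinence at 12 months is CO validated (section 6.5). An embargo could delay release of the primary result, which the two-stage design exists to provide. That is a debatable trade-off, not a correction.

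**Conclusion.** The point holds as a moderate correction. The stated SAP milestone, read literally, falls about six months (184 days) after the primary data are complete, with perhaps 3 to 5 of those months after the result is known if cleaning and analysis take 1 to 3 months.

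The conclusion rests on reading data collection as including the 12-month data, which the live database and section 10.5 support, and on the planned dates being kept. If recruitment slips, both milestones move together and the order remains.

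The exposure is confined to the items marked open or undefined in the table. Among them, the convergence fallback and the later-contact rule matter most because they can reach the primary result. It would go too far to say that the headline test is unprotected or that the SAP was written after the result.

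**What to change.** In section 12.4, replace the SAP milestone with: *finalised and signed off before the 6-month soft lock and before any extraction or summary of outcome data by arm*. Agreement by the steering and management committees stays as it is.

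The cost is one sentence and an earlier sign-off, with correspondingly less freedom to revise the plan late. It needs no extra data or staff and changes neither sample size nor power. The open items above can then be settled in the SAP, where they belong, provided it is signed by that date.

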13.1 Participants and Recruitment

We propose a quota sampling approach to recruit HCPs in order to capture a range of views and the perspectives of practitioners who would be in a position to refer smokers to an EC helpline in future, should the results of the trial be positive.

Following relevant recommendations on sample size in qualitative interview studies (24), a group of 20 HCPs in a variety of different roles, all of whom treat smokers on a regular basis, should be sufficient to obtain a variety of perspectives and identify relevant barriers and facilitators regarding future referral pathways. From within the trial, LCRN research nurses will assist with identifying HCPs at study recruitment sites, provide them with information about the qualitative study and seek consent to pass their contact details onto the research team. If trial recruitment also occurs in primary care, practices involved in the trial will also be informed about the qualitative element and GPs working in the practice will be invited to participate in a short interview. Further recruitment from outside the trial will draw on clinical and practice networks that [name] (who will lead the qualitative element) is involved in. This includes training workshops she delivers to GPs on cancer prevention in partnership with the Royal College of GPs and Cancer Research UK; collaborations with dental academics and involvement in CPD provision for dentists; and involvement in CPD provision for a range of other HCPs in her role as an Honorary Consultant in Public Health for NHS Lothian.

Twelve participants involved in the study (both smokers and recent ex-smokers) will be recruited. Eight smokers not participating in the trial will be recruited via the UKCTAS tobacco and nicotine discussion group (25), flyers at community venues in London and Edinburgh and, if required, via social media. To facilitate recruitment, a £20 voucher (which cannot be used to purchase tobacco) will be provided regardless of involvement in the study.

HCPs and smokers not involved in the main trial who are interested in taking part will be given a sub study PIS and contact by the research team at the University of Edinburgh to arrange a suitable time to conduct the interview. All main trial participants will be informed about the sub study when they consent to the main

study and will be asked if they are happy to be contacted for an interview if selected. The Edinburgh study team will contact a selection of those who agreed (based on quota sampling) at around 4 weeks post TQD and invite them to take part. Those who are still interested will be emailed the PIS and a convenient time to conduct the interview will be arranged. All sub study participants will give verbal informed consent which will be recorded electronically. Participants will be emailed or posted a copy of their consent form.

13.2 Procedures and Analysis

Semi-structured interview topic guides will be developed for each group of interviewees and piloted prior to use. For HCPs, the interviews will focus on current contact with smokers, existing referral routes, awareness and views regarding EC, mechanisms for referral to an EC helpline if available in future outside of the trial, willingness to refer to an EC helpline and practical issues that may arise. Previous experience suggests HCPs may not consent to long interviews so these will be limited to around 20 minutes. For smokers and quitters, tailored topic guides will be developed to assess their experience of relevant procedures and treatments and their views on EC helpline use. It is anticipated these interviews will take 30-40 minutes. For smokers not involved in the trial the topic guide will focus on willingness to access an EC helpline if available and barriers and facilitators to accessing and using it.

Interviews will be conducted by telephone/Zoom/Skype in most cases to minimise travel costs and to limit any COVID related restrictions but where required and appropriate face to face interviews will be offered. All interviews will be recorded and transcribed. Transcripts will be entered into NVivo 11 and analysis will take an inductive thematic coding approach to explore views and opinions (26).

14. Economic Analyses

A 'within-trial' incremental cost-effectiveness analysis will be undertaken using 'cost-per-quitter' as used in the primary outcome measure for the trial. The incremental costs and benefits of the treatment arms (EC and EC+) compared with the control arm will be reported using an incremental cost-effectiveness ratio (ICER) where appropriate using 12 month follow up cost and outcome data.

Intervention costs will be prospectively recorded alongside the trial. These include costs of providing EC and the costs of the helpline support service (staff time, costs of maintaining service). We will also record and value the costs of training in the treatment arms, which includes costs outside the other trial arms. We will contact the providers of the Live Well programme to help derive costs of service provision in the control arm. The costs of e-liquid refills paid for by participants will also be recorded.

The Health service use questionnaire will be used to measure participants' utilisation of wider health care resources in each trial arm at baseline and each follow-up point,

with national average unit costs (27, 28) applied to quantities to derive a health care cost profile. We will use an NHS and PSS perspective as recommended by NICE.

The cost-effectiveness analysis combines intervention costs and wider health care costs with the number of quitters to calculate the cost per quitter of the intervention over and above usual care.

We will also present a cost-utility analysis using cost per QALY within the one year trial period. EQ-5D-5L is administered at baseline and each follow-up to enable to computation of Quality Adjusted Life Years (QALYs) (29) derived by using the area under the curve based on EQ-5D-5L score at each time point (30). We will use the tariff recommended by NICE at the time of analysis to derive health utilities from the EQ-5D-5L responses.

Missing data in smoking status will be treated as per the statistical analysis to keep the results consistent. Missing data in other variables will be handled using multiple imputation imputation assuming missing at random (MAR). The primary analysis will be performed based on imputed dataset following Rubin's rule (31). We will explore the impact of uncertainty with the construction of cost-effectiveness acceptability curves derived by non-parametric bootstrapping for the 'within-trial' analysis (32). The impact of MAR assumption will be assessed in sensitivity analysis.

15. Ethics

The trial will only proceed after obtaining relevant ethical approvals from the National Research Ethics Committee and Health Research Authority (HRA) and it will be conducted in accordance with GCP guidelines. As the trial does not include any investigational medicinal product and the Medicines and Healthcare products Regulatory Agency (MHRA) have previously confirmed to us that EC trials do not require their involvement, MHRA approvals are not required.

16. Public Involvement

The proposal has been discussed with the UK Centre for Tobacco and Alcohol Studies public engagement group of smokers, ex-smokers and vapers (25) (now under the new SPECTRUM consortium). We have sought guidance on the study protocol and development of participant documents. The group will be consulted on the study progress annually about trial progress and results and input will be sought on developing a dissemination strategy for the results.

The project will also be discussed at future annual Stop Smoking Service (SSS) update and supervision events and we will seek input particularly on the qualitative aspect of the study based on advisors' experience.

Two smokers from these panels and an SSS specialist will be invited to join the Trial Steering Committee which will meet during the pilot phase and every 12 months thereafter.

17. Data handling and record keeping

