6.1 Aims

The proposed research aims to answer three questions:

- 1) What is the effectiveness and cost-effectiveness of EC provided with no additional treatment compared to the most economical standard care option?
- 2) To what degree is effectiveness of EC enhanced by telephone counselling via EC-specific helpline and how does this affect the intervention cost-effectiveness?
- 3) What are the barriers and facilitators to referral by HCPs of smokers interested in EC to an EC helpline, and for smokers using it?

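### Section 14 sets the cost-effectiveness ratios of EC and EC+ against control and does not pre-specify EC+ versus EC, the increment that Aim 2 asks about

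*Protocol*

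**What the plan says.** Section 6.1 (Aims) poses two economic questions. The first is "What is the effectiveness and cost-effectiveness of EC provided with no additional treatment compared to the most economical standard care option", that is, EC against QN. The second is "To what degree is effectiveness of EC enhanced by telephone counselling via EC-specific helpline and how does this affect the intervention cost-effectiveness", that is, the effect of adding the helpline to EC. Section 12.3 follows the same structure: its two pairwise comparisons, with the Bonferroni adjustment, are QN versus EC and EC versus EC+.

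Section 14 does not follow it. It plans to report, as an incremental cost-effectiveness ratio, the "incremental costs and benefits of the treatment arms (EC and EC+) compared with the control arm". Further on, it combines costs with numbers of quitters "to calculate the cost per quitter of the intervention over and above usual care". These are the only two sentences in the section that name a comparator, and both name control or usual care. The cost-utility sentence, "We will also present a cost-utility analysis using cost per QALY within the one year trial period", names none, and the acceptability curves are described without saying which arms they cover.

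On the outcome, section 14 takes cost per quitter "as used in the primary outcome measure for the trial", which section 6.4 places at 6 months, and then reports the ratios "using 12 month follow up cost and outcome data".

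**The concern.** QN, EC and EC+ are mutually exclusive options of rising intensity, and EC+ is the EC package plus five support calls (section 10.1). A commissioner deciding whether to fund a helpline needs the extra cost and extra benefit of EC+ over EC. EC+ against QN answers a different question, because it pools the return on the starter pack with the return on the calls. If the starter pack is cheap and effective, the pooled ratio can look acceptable while the calls buy extra quitters at a much higher price. If the calls are the cheaper step, the pooled ratio undersells them. In either case the economic half of Aim 2 has no pre-specified estimate, and the comparison would be chosen after results are known.

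**Working it through.** **Inputs.** Quit rates are from section 12.1: planned 6% (QN), 15% (EC), 25% (EC+); more modest 6%, 12%, 20%. The protocol states no economic figure to reproduce. The sample sizes built on the planned rates do reproduce (two-sided alpha 0.025, 90% power): 25% v 15% gives 391 per arm with unpooled variance (stated 390), and 15% v 6% gives 286 with pooled variance (stated 286). The protocol gives no unit costs, so these are assumptions: c is the net extra cost per participant of EC over QN, and h is the net extra cost of the helpline over EC.

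**Formulae at the planned rates.**
- EC v QN = c / (0.15 − 0.06) = c / 0.09
- EC+ v EC = h / (0.25 − 0.15) = h / 0.10
- EC+ v QN = (c + h) / (0.25 − 0.06) = (c + h) / 0.19

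The last is a weighted average of the first two, with weights 0.09/0.19 = 47% and 0.10/0.19 = 53%. Check with c = £40, h = £100: 0.474 × £444 + 0.526 × £1,000 = £737 = £140/0.19.

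**Direction.** EC+ v QN lies below EC+ v EC only when h/0.10 > c/0.09, that is, h > 1.11c. At the modest rates the condition is h/0.08 > c/0.06, that is, h > 1.33c.

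**Size, with c = £40 and h from £60 to £200 (cost per quitter).**

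| Quit rates QN/EC/EC+ | h | EC v QN | EC+ v QN | EC+ v EC | (EC+ v EC) ÷ (EC+ v QN) |
|---|---|---|---|---|---|
| 6/15/25% | £60 | £444 | £526 | £600 | 1.14 |
| 6/15/25% | £100 | £444 | £737 | £1,000 | 1.36 |
| 6/15/25% | £200 | £444 | £1,263 | £2,000 | 1.58 |
| 6/12/20% | £60 | £667 | £714 | £750 | 1.05 |
| 6/12/20% | £100 | £667 | £1,000 | £1,250 | 1.25 |
| 6/12/20% | £200 | £667 | £1,714 | £2,500 | 1.46 |
| 6/15/18% (assumed) | £60 | £444 | £833 | £2,000 | 2.40 |
| 6/15/18% (assumed) | £100 | £444 | £1,167 | £3,333 | 2.86 |
| 6/15/18% (assumed) | £200 | £444 | £2,000 | £6,667 | 3.33 |

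The 18% in the last three rows is not in the protocol; it shows what happens if the helpline adds only 3 points.

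**Reversal.** With c = h = £60 at 6/15/25%, EC v QN is £667, EC+ v QN £632 and EC+ v EC £600, so the control-based ratio now overstates the cost of the helpline step.

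**Consequence for a decision.** In the second row, any willingness to pay between £737 and £1,000 per quitter would accept EC+ against control and reject the helpline as an addition to EC.

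**The case against.** The best defence is that the comparison can be recovered. Incremental costs and benefits of EC and EC+ are both taken against the same control arm, so subtracting them gives the EC+ versus EC point estimate, and helpline costs are recorded separately. This stands as far as it goes: a reader might infer that Aim 2 can never be answered, and the protocol does not support that. What is missing is a pre-specified ratio with its uncertainty. The two control-based contrasts share the QN arm, so the uncertainty of their difference cannot be read from two separate ratios.

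Aim 2 could also be read as asking how value against usual care changes when the helpline is added. The wording allows this, but it would leave the economics out of line with section 12.3, where EC versus EC+ is a main comparison.

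The cost-utility analysis and the acceptability curves name no comparator, so they do not exclude a three-arm analysis, and a later analysis plan might supply one. Layout and dominance rules can fairly be left to such a plan. The point here is narrower: where section 14 does fix a comparator, it fixes control.

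A reader might infer that EC+ will look good value when the helpline is not. That is conditional, as the reversal shows. The primary analysis also offers some protection. At 15% v 18% with 390 per arm, the standard error is √((0.15×0.85 + 0.18×0.82)/390) = 0.0266, and 0.03/0.0266 − 2.241 = −1.11, a power of about 13%. The trial would then probably report no significant helpline effect beside the economics.

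Two readings of the time point also go too far. One is that section 14 gives the quitter two conflicting definitions. Section 6.5 gives one definition of sustained abstinence for all follow-ups, so the natural reading is the same kind of outcome measured at 12 months; the wording is loose. The other sets the earlier trial's 35% at 6 months (section 12.1) against its 18% at one year (section 5) and infers that cost per quitter nearly doubles. Those are one arm's rates, they are not shown to be the same measure, and the ratio depends on differences between arms.

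**Conclusion.** The point holds as a mismatch between Aim 2 and section 14: EC+ versus EC is not pre-specified in the economic analysis, and EC+ versus QN is not a substitute for it. At the protocol's own quit rates the helpline's cost per extra quitter is 5% to 58% above the control-based figure, given the assumed £40 and £60 to £200. The gap is larger if the helpline adds little, and the sign reverses if the helpline is cheap relative to the starter pack. All costs are assumptions, and the quit rates are 6-month planning values whereas the economic analysis uses 12-month data, so the sizes are illustrative; the weighted-average argument does not depend on the particular costs. Cost-effectiveness is a secondary endpoint, and design, conduct and the primary analysis are untouched. This is a should-fix.

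**What to change.** In section 14, replace the control-only comparison with a fully incremental analysis of QN, EC and EC+: order the arms by cost, check for dominance and extended dominance, and report EC v QN and EC+ v EC, each per quitter and per QALY and with uncertainty from the planned bootstrap. Include all three arms in the acceptability curves. EC+ v QN may stay as a supplementary result. As a minor clarification, state that the quitter in the 12-month analysis is the 12-month CO-validated sustained abstainer.

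Helpline costs, health service use, EQ-5D-5L and quit status are already to be collected, so the change costs a few sentences and a small amount of analysis time. It should be made before the economic results are seen.
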